2.5 Data Monitoring Committee and Other External Committees

The SSC will closely review the safety data throughout the study to provide guidance and scientific expertise on the risk/benefit ratio in general and for the separate prospective subgroups following a predefined Safety Management Plan respecting the data for rate and frequency of Grade 3 and 4 select adverse events (estimated <25%) and QoL (patient-reported outcomes).

3 OBJECTIVES

3.1 Primary Objective

To determine the incidence of high-grade (CTCAE v4.0 Grades 3-4), treatment-related, select adverse events in subjects with advanced or metastatic SqNSCLC who progressed during or after at least 1 systemic therapy.

3.2 Secondary Objective

- To determine the incidence and to characterize the outcome of all high-grade (CTCAE v4.0 Grades 3-4), select adverse events in subjects with advanced or metastatic SqNSCLC who have progressed during or after at least 1 prior systemic therapy
- To estimate overall survival (OS) in all treated subjects
- To estimate investigator-assessed objective response rate (ORR)

[REDACTED]

4 ENDPOINTS

4.1 Primary Endpoints

The primary endpoint is the incidence of high-grade (CTCAE v4.0 Grades 3-4 or higher), treatment-related, select adverse events.

4.2 Secondary Endpoints

The secondary endpoints include:

- Incidence of high grade (Grade 3-4) select adverse events
- Median time to onset and median time to resolution (Grades 3-4) of select adverse events
- OS is defined as the time from first dosing date to the date of death. A subject who has not died will be censored at last known date alive. OS will be followed continuously while subjects are on treatment and every 3 months via in-person or phone contact after subjects discontinue the study drug.
- ORR is defined as the number and percentage of subjects with a best overall response (BOR) of confirmed CR or PR with respect to all treated subjects. ORR as assessed by the investigator will be reported.

[REDACTED]

5 SAMPLE SIZE AND POWER

The total sample size for this study is based on logistical considerations. Nevertheless, certain statistical properties of the projected sample size are indicated below.

A total of 950 subjects who are evaluated based on the ECOG PS will be enrolled, and a minimum of 30% (285 subjects) should present with PS2. In addition, a minimum of 40% of patients should be enrolled as second-line, and a minimum of 40% of patients should be enrolled as third-line. With a 15% screen failure rate, a total of approximately 800 subjects will be treated. If the true cumulative incidence rate is 0.5 then with $n = 800$ subjects, about 3 subjects will experience a rare adverse event (with a 95% confidence interval (CI) of 0.1%-1.3%) for the cumulative incidence rate. If the assumed true event rate is 0.3% then approximately 3 subjects will experience events with a 95% CI of 0.1%-0.8% for the assumed true event rate. In addition, with 800 subjects, the probability of observing at least one rare event (with 0.3% true rate) is 91.0%.

The 95% CI is calculated using the Clopper-Pearson method.

6 STUDY PERIODS, TREATMENT REGIMENS AND POPULATIONS FOR ANALYSES

6.1 Study Periods

See Core Safety SAP.

6.2 Treatment Regimens

Subjects will be treated with 3 mg/kg of nivolumab as a 60-minute IV infusion (+/-5 min) on Day 1 +/- 2 of a treatment cycle every 2 weeks (14 days) until progression, unacceptable toxicity, or withdrawal of informed consent. No premedications are recommended for the initiation of dosing. Dosing calculations should be based on the body weight assessed at each visit. All doses should be rounded to the nearest milligram. The screening body weight may be used for dosing of Cycle 1. There will be no nivolumab dose escalations or reductions permitted. Subjects may be dosed no fewer than 12 days from the previous dose.

6.3 Populations for Analyses

- All enrolled subjects: all subjects who signed an informed consent form and were registered into the IVRS.
- All treated subjects: all subjects who received any nivolumab. This is the primary population for safety and efficacy analyses.
- All response evaluable subjects: all treated subjects who have baseline and at least one on-study tumor measurement.

See section 7.1 for the subpopulation details.

7 STATISTICAL ANALYSES

7.1 General Methods

In the analysis described below (except where noted), counts and percentages will be reported for discrete variables with inclusion of unknown or missing values as a separate category. The mean, standard

deviation, median, range (minimum and maximum), and number of non-missing values will be reported for each continuous measure.

Adverse events and medical history will be coded according to the most recent Medical Dictionary for Regulatory Activities (MedDRA). Previous and concomitant medications will be coded using the WHO Drug Dictionary.

The time to event distribution (i.e overall survival and duration of response) will be estimated using Kaplan Meier techniques. Median for time to event endpoints along with 95% confidence interval (CI) will be constructed based on 95% CI using the Brookmeyer and Crowley method. OS rates at selected time points, including survival rates at Years 1 and 2, together with their 95% CIs will also be estimated using KM estimates on the OS curves. Associated 2-sided 95% CIs will be calculated using the Greenwood formula.

The analysis of primary, secondary (excluding objective response rate), and exploratory endpoints will be reported for the treated population and subgroups based on ECOG PS (PS 0-1 and PS 2). ORR will be reported for the response evaluable analysis set and by ECOG PS subgroups.

SAS® version 9.2 or higher will be used for statistical analyses, tabulations and graphical presentations.

7.2 Study Conduct

7.2.1 Accrual

The accrual pattern will be summarized per country, investigational site and per month for all enrolled subjects. Informed consent date, first dosing date, country, and investigational site will be presented in a by subject listing of accrual.

7.2.2 Relevant Protocol Deviations

The relevant Protocol Deviations will be summarized for all enrolled subjects. The following programmable deviations from inclusion and exclusion criteria will be considered as relevant protocol deviations. Non-programmable relevant eligibility and on-treatment protocol deviations, as well as significant (both programmable and non-programmable) eligibility and on-treatment protocol deviations will be reported through data management listings.

At entrance:

- Subjects with any NSCLC histology other than squamous cell.
- Subjects without measurable disease at baseline.
- Subjects who did not meet prior therapy restrictions.

On-study:

- Subjects receiving concurrent anti-cancer therapy (defined as chemotherapy hormonal immunotherapy, radiation therapy, standard or investigational agents for treatment of NSCLC).
- Subjects treated differently from enrolled (subjects who received the wrong treatment, excluding the never treated).

A subject listing will also be produced.

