3.3.1 Inclusion Criteria

1) Signed Written Informed Consent

- a) Subjects must have signed and dated an IRB/IEC-approved written informed consent form in accordance with regulatory and institutional guidelines. This must be obtained before the performance of any protocol-related procedures that are not part of normal subject care.
- b) Subjects must be willing and able to comply with scheduled visits, treatment schedule, laboratory tests, and other requirements of the study.

2. Target Population

- a) ECOG PS:
 - i) PS 0 to 1 (Subgroup 1)
 - ii) PS 2 (Subgroup 2; minimum of 95 enrolled (81 treated) subjects. The Scientific Steering Committee will provide guidance and scientific expertise on the risk/benefit ratio following a Safety Management Plan).
- b) Subjects with histologically or cytologically-documented SqNSCLC who presented with stage IIIb/stage IV disease or who developed recurrent or progressive disease following prior definitive therapy for localized or local advanced disease. NOTE: A fresh biopsy is not required to take part in the study.
- c) Subjects must have experienced disease recurrence or progression during or after one prior platinum doublet-based chemotherapy regimen for advanced or metastatic disease.
 - i) Maintenance therapy following platinum doublet-based chemotherapy is not considered as a separate regimen of therapy
 - ii) Subjects who received platinum-containing adjuvant, neoadjuvant or definitive chemoradiation therapy given for locally advanced disease, and developed recurrent (local or metastatic) disease within 6 months of completing therapy are eligible.
 - iii) Subjects with recurrent disease > 6 months after platinum-containing adjuvant, neoadjuvant or definitive chemoradiation therapy given for locally advanced disease, who also subsequently progressed during or after a platinum doublet-based regimen given to treat the recurrence, are eligible.
- d) Subjects must have evaluable disease by CT or MRI per RECIST 1.1 criteria (radiographic tumor assessment performed within 28 days of first dose of study drug) or clinically apparent disease that the investigator can follow for response.
- e) Subjects with CNS metastases:

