5.4 Efficacy Assessments

Mandatory tumor assessments are to be done at Weeks 9 and 52 (± 5 days), and additional tumor assessments should be performed as required by local standards of care or at the investigator's discretion as discussed in [Table 5.1-2](#) and are recommended every 8-12 weeks until:

- Disease progression per RECIST 1.1 criteria (or discontinuation of study treatment in subjects receiving nivolumab beyond progression)
- Subject lost to follow-up
- Withdrawal of study consent by subject
- End of study

Study evaluations will take place in accordance with [Table 5.1-2](#) and should be performed according to RECIST 1.1 criteria.

High resolution CT with oral or IV contrast or contrast-enhanced MRI are the preferred imaging modalities for assessing radiographic tumor response. If a subject has a known allergy to contrast material, please use local prophylaxis standards to obtain the assessment with contrast if at all possible or use an alternate modality. In cases where contrast is strictly contraindicated, a non-

contrast scan will suffice. Screening assessments, including chest, abdomen, pelvis, brain, and all known or suspected sites of disease, should be performed within 28 days of first dose of study drug. Brain MRI is the preferred imaging method for evaluating CNS metastasis. In addition to chest and abdomen, all known or suspected sites of disease (including CNS) should be assessed at subsequent assessments using the same imaging method and technique. If more than one method is used at screening, then the most accurate method according to RECIST 1.1 should be used when recording data and should again be used for all subsequent assessments. Bone scan, PET scan, or ultrasound is not adequate for assessment of RECIST response. In selected circumstances where such modalities are the sole modality used to assess certain non-target organs, those non-target organs may be evaluated less frequently. For example, bone scans may need to be repeated only when complete response is identified in the target disease or when progression in bone is suspected. Previously treated CNS metastases are not considered measurable lesions for purposes of RECIST determined response.

Tumor measurements should be made by the same investigator or radiologist for each assessment whenever possible. Changes in tumor measurements and tumor responses to guide ongoing study treatment decisions should be assessed by the investigator using RECIST 1.1.

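### SAP 7.2.2 treats absence of measurable disease as an eligibility deviation, but the protocol admits evaluable or clinically apparent disease, so eligible subjects are counted as deviators

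*SAP*

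**What the plan says.** SAP 7.2.2 (Relevant Protocol Deviations) introduces its list with "The following programmable deviations from inclusion and exclusion criteria will be considered as relevant protocol deviations". The second of the three entrance items is "Subjects without measurable disease at baseline". On reporting it states: "The relevant Protocol Deviations will be summarized for all enrolled subjects", and then "A subject listing will also be produced". Eligibility deviations that cannot be programmed go to data management listings.

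Protocol 3.3.1, inclusion criterion 2d, offers two routes to eligibility. The first is "Subjects must have evaluable disease by CT or MRI per RECIST 1.1 criteria", with imaging in the 28 days before first dose. The second is "or clinically apparent disease that the investigator can follow for response". Table 5.1-1 repeats both routes in its baseline tumor assessment row. No visible inclusion or exclusion criterion requires measurable disease.

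**The concern.** The SAP list is meant to capture departures from the protocol's own criteria. This item tests something stricter than the criterion it stands for. A subject can satisfy 2d in full and still be programmed as an entry deviation.

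What is at stake is the accuracy of the deviation table. The protocol closes its eligibility section by stressing that every criterion must be met in full, and this table is one of the places where the report shows whether that happened. A count that mixes eligible subjects with true failures makes compliant sites look non-compliant. It also leaves a reader unable to tell how many subjects really lacked the disease that 2d requires.

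**Working it through.** The plan states no figure to reproduce. The check is a comparison of wording, followed by a simple set argument.

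**1. Are the two terms interchangeable in these documents?** No. Protocol 5.4 uses *measurable* as the narrower term: "Previously treated CNS metastases are not considered measurable lesions for purposes of RECIST determined response". Protocol 4.6.6 likewise refers specifically to new measurable lesions when it defines further progression. Criterion 2d uses *evaluable* and then adds a clinical route that does not depend on radiographic measurement.

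**2. Whom does each rule accept?** Let M be measurable disease, E evaluable disease on CT or MRI, and C clinically apparent disease that can be followed.

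| Subject at baseline | Protocol 2d (E or C) | SAP 7.2.2 (flag if not M) | Result |
|---|---|---|---|
| M | eligible | not flagged | agree |
| E, not M | eligible | flagged | false deviation |
| C only | eligible | flagged | false deviation |
| neither E nor C | not eligible | flagged | agree |

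The last row follows because measurable disease is a form of evaluable disease. A subject with neither E nor C therefore cannot have M. The SAP rule flags every subject in the last three rows under one label, although only the last row fails 2d. The table covers the disease element of 2d only. The 28-day imaging window is a separate element that this bullet does not address.

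**3. How many subjects?** The documents do not give the share with only non-measurable disease, so the number cannot be derived. The base for illustration is the 950 planned enrolled subjects, because 7.2.2 summarizes deviations for that population and not for the roughly 800 treated.

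- Assumed share 1%: 0.01 × 950 = 9.5, about 10 subjects.
- Assumed share 10%: 0.10 × 950 = 95 subjects.

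These are scale markers, not estimates.

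**4. Does anything downstream depend on the flag?** SAP 6.3 defines three populations: enrolled, treated and response evaluable. None excludes a subject for a deviation, and the visible SAP has no per-protocol set. Treated subjects are the primary population for safety and efficacy. Membership of the response evaluable set depends on having baseline and on-study tumor measurements. The primary endpoint, OS and ORR are therefore the same with or without the flag.

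**The case against.** Four points can be made for leaving the item alone.

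*Measurability matters for ORR.* It does, but its absence is not an eligibility failure under 2d. Assessability for ORR is handled by the response evaluable set, and SAP 7.3.2 already lists baseline tumor assessment among the summarized characteristics.

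*The effect is small.* This stands. One row of a descriptive table and the matching listing entries are affected. Other outputs, namely the data management listings and the baseline tumor assessment, would help a careful reader separate the groups.

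*The SAP may have matched its own protocol version.* SAP 2.4 says it is based on Revised Protocol 03, and the protocol in hand is later. The wording of 2d in Revised Protocol 03 cannot be checked, and part of the entry for Amendment 04 is redacted. The visible change log reports no later change to this criterion. In either case the rule does not match the current protocol.

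*A corrected rule may not be programmable.* This also stands in part. Whether disease is clinically apparent and can be followed is an investigator's judgment, and the documents show no CRF field for it. The fix has to allow for that.

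A reader might go further and infer that the rule misses genuine breaches of the disease requirement. It does not: a subject with neither kind of qualifying disease also lacks measurable disease and is flagged. The fault is over-capture. A reader might also infer that efficacy or safety results are distorted, or attach a firm count of misclassified subjects. The documents support neither.

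**Conclusion.** The mismatch is real and modest in effect. The deviation summary and listing, run as written, would count eligible subjects with only non-measurable disease as relevant deviations and would not distinguish them from true failures of 2d. Any non-zero share of such subjects makes the count wrong; by how much is unknown.

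The conclusion rests on two things: the current wording of 2d and Table 5.1-1, and the absence of any visible criterion requiring measurable disease. It carries the caveat that the version of 2d on which the SAP was built is not available.

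**What to change.** Reword the entrance item in SAP 7.2.2 so that it is the complement of inclusion 2d, and cite the criterion. A subject is flagged only when both routes fail at baseline: no evaluable disease on CT or MRI under RECIST 1.1, and no "clinically apparent disease that the investigator can follow for response".

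If the second route cannot be derived from the database, program the imaging part only as a screen. Settle the clinical part through the non-programmable eligibility deviations already provided for in 7.2.2, and count a subject only after that review.

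If the team wants measurability on record, report measurable disease (yes/no) under Baseline Tumor Assessment in SAP 7.3.2.

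The cost is one SAP line and its program, plus case review where the clinical route applies. No protocol change is needed and no endpoint analysis is touched. It should be done before the deviation program is run.

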7.3 Study Population

7.3.1 Subject Disposition

The total number of subjects enrolled in the study will be presented.

Number of subjects enrolled but not treated along with the reason will be tabulated. This analysis will be performed on the enrolled population only.

Number of subjects who discontinued study treatment along with corresponding reason will be tabulated using the enrolled population.

A subject listing for all enrolled subjects will be provided showing the subject's off study date and reason for going off-study. A subject listing for subjects not treated will also be provided, showing the subject's race, sex, age, consent date and reason for not being treated.

7.3.2 Demographic Characteristics

Demographic characteristics such as gender, age, race and ethnicity will be listed for all treated subjects. Demographic characteristics will also be summarized for all treated subjects.

The following characteristics will be summarized and listed:

- Age in years
- Age category (< 65, >= 65 to 75, >=75 to < 85, >=85, >=75, >=65 years)
- Gender, Race/Ethnicity
- ECOG PS (0-1, 2)
- Country
- Baseline weight
- Baseline height
- Baseline BMI
- Smoking Status
- Baseline Tumor Assessment
- Lung Cancer Symptom Score
- Baseline HIV result
- Baseline mutation status (EGFR, ALK, ROS, MET, KRAS, BRAF)
- CNS metastasis (Yes, No)
- Current disease stage (IIIB, IV)
- Cardiac insufficiency category by NYHA
- Type of prior cancer regimen (adjuvant, neo-adjuvant, metastatic disease)
- Time from diagnosis to enrollment
- Baseline Vital Sign (Temperature, BP, HR, RR) and Oxygen Saturation. Age will be calculated as follows: Age = maximum integer \leq $([\text{Date of informed consent} - \text{Date of Birth} + 1] / 365.25)$.

7.3.3 Medical history – Concurrent diseases

General medical history will be listed by subject and pretreatment events will be tabulated for all treated subjects.

7.3.4 Baseline Examinations

Subjects with abnormal baseline physical examination will be tabulated and listed by examination criteria using the treated population.

7.3.5 Prior Therapy Agent

Prior therapy will be summarized for all treated subjects.

The following information will be presented:

- Prior therapy (yes or no).
- Setting of prior systemic therapy regimen received (adjuvant, metastatic disease, neo-adjuvant).
- Best response to most recent prior regimen (CR/PR vs SD vs PD).
- Time from completion of most recent regimen to treatment (<3, 3-6, >6 months).
- Time from completion of prior adjuvant/neo-adjuvant therapy to treatment (subjects who received prior adjuvant/neo-adjuvant), (<6 months and >=6 months).
- Prior surgery related to cancer (yes or no)
- Prior radiotherapy (yes or no)
- Prior systemic therapy classified by therapeutic class and generic name
- Prior/current non-study medication classified by anatomic and therapeutic classes.

Agents and medication will be reported using the generic name. A listing by subject will also be provided for prior systemic cancer therapy, prior radiotherapy, prior surgery related to cancer and non-study medication.

7.4 Extent of Exposure

Analyses in this section will be performed in all treated subjects.

7.4.1 Administration of study therapy

The analysis of study drug exposure will focus on the on-study period. The first dosing day corresponds to the day of first administration of nivolumab. Throughout this analysis plan, nivolumab dose level will refer to the actual dose received rather than the planned dose. The dose level will be in mg/kg.

Subjects will be treated with 3 mg/kg of nivolumab as a 60-minute IV infusion (+/- 5 min) on Day 1+/-2 of a treatment cycle every 2 weeks (14 days) until progression, unacceptable toxicity, or withdrawal of informed consent.

The following parameters will be summarized (descriptive statistics) for all treated subjects:

- Relative dose intensity (%) using the following categories: < 50%; 50 - < 70%; 70 - < 90%; 90 - < 110%; ≥ 110%.
- Number of doses received (summary statistics)

- Cumulative dose
- Duration of treatment: duration of treatment will be presented using a Kaplan-Meier curve whereby the last dose date will be the event date for subjects who discontinued study therapy. Subjects who are still on study therapy will be censored on their last dose date. Also, duration of therapy will be presented according to the following: >3 months, >6 months, >9 months, and >12 months.

A by-subject listing of extent of exposure: weight, number of doses, date of first and last dose, duration of treatment, dose delay, reason for delay and reason for discontinuation.

Table 2: Administration of study therapy: definition of parameters

nivolumab	
Dosing schedule per protocol	3 mg/kg every 2 weeks
Dose	Dose (mg/kg) is defined as Total Dose administered (mg)/Most recent weight (kg). Dose administered in mg at each dosing date and weight is collected on the CRF.
Cumulative Dose	Cumulative dose (mg/kg) is sum of the doses (mg/kg) administered to a subject during the treatment period.
Relative dose intensity (%)	$[\text{Cumulative dose (mg/kg)} / ((\text{Last dose date} - \text{Start dose date} + 14) \times 3/14)] \times 100$
Duration of treatment	Last dose date – Start dose date +1

